2. Clinical effectiveness: Primary analysis for clinical effectiveness will include only those initiating the regimen per label i.e. initiating CAB+RPV LA with VL<50 copies/mL at regimen initiation. The following VL measures will be used for effectiveness assessment:

- 1. Proportion of individuals, virologically suppressed/undetectable (<50 copies/mL) at 6, 12 and 24 months following initiation of CAB+RPV LA regimen
- 2. Proportion of individuals with VL <200 copies/mL at 6, 12 and 24 months following initiation of CAB+RPV LA regimen
- 3. Proportion of individuals with confirmed virologic failure (CVF) during the first 6 months, and at 6, 12 and 24 months following initiation of CAB+RPV LA regimen defined as:
 - Two consecutive HIV RNA VL levels ≥200 copies/mL or
 - One HIV RNA VL level ≥200 copies/mL and regimen discontinuation within 4 months of VL ≥200 copies/mL

3. Resistance Testing:

Since this is a non-interventional study aiming to capture individual care in real world setting, the study will not mandate resistance testing following discontinuation of CAB+RPV LA regimen. Health care providers following the local treatment guidelines decide what laboratory and resistance tests are to be conducted. Data thus generated, including available HIV-1 subtypes, will be captured and analyzed by the study team.

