Non-adherence to dosing schedule will be assessed by estimating the number of individuals that missed one or more consecutive injections without taking daily oral bridging therapy or any other oral ARV regimen while not on CAB+RPV LA regimen and median number of injections missed during a 12-month period. We will also estimate the number who received the injections seven or more days later than their scheduled injection visit and median duration of delayed injections in persons using bridging therapy. In addition, the number of individuals who missed one or more consecutive injections without taking daily oral bridging therapy or those who received the injections seven or more days later than their scheduled injection visit will be assessed and patient characteristics for those individuals that are non-adherent will be described.

Logistic regression will be used to identify factors associated with not starting CAB+RPV LA in those that start lead in, to compare those missing injections where bridging treatment is used, non-adherence and to identify factors associated with discontinuation of CAB+RPV LA (when there are more than 30 endpoints). Potential explanatory variables are listed above. The model building strategy will follow EuroSIDA protocol and include variables significant in univariate analyses as well as *a priori* pre-specified variables of interest.

AIM 3. Assess the clinical effectiveness (i.e. proportion individuals experiencing virologic failure and proportion with undetectable VL) among PLWH who initiate CAB+RPV LA regimen

The study will estimate the proportion with virologic failure during the first six months and at six, twelve and twenty four months after the start of the treatment with injectable regimen. Given that this study involves persons in routine clinical care, and who may not attend clinic appointments at 6, 12 or 24 months, a window of 12 weeks around the date in question will be used for virologic failure. Thus, the proportion with virologic failure during first six months, at 6, 12 or 24 months \pm 6 weeks will be used; and if none is available, the first measurement during first six months, after 6, 12 or 24 months (and at most 6 weeks after the measurement).

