Descriptive analyses will compare those with and without virologic failure to assess any differences in baseline characteristics of the two groups. Detailed analysis of additional risk factors will be limited to persons with 6, 12 or 24 months of follow-up. Multivariable logistic regression models will investigate the factors associated with virologic failure at 6 months, 12 months and 24 months after CAB+RPV LA initiation. Potential explanatory variables are listed above. We will also investigate the impact of missed doses and use of oral bridging therapy by using the data collected via the CRF. Multivariate analyses will be performed when > 30 persons on CAB+RPV LA have virologic failure and analyses will be limited to persons with > 6-, 12- or 24-months follow-up. The model building strategy will follow EuroSIDA protocol and include variables significant in univariate analyses as well as *a priori* pre-specified variables of interest. Primary analysis for clinical effectiveness will include individuals on CAB+RPV LA, with VL of <50/copies/mL at regimen initiation. In addition, all the analyses will be conducted separately for individuals on CAB+RPV LA with VL of ≥50 copies/mL at regimen initiation.

Our primary analyses of virologic outcomes will censor follow-up at discontinuation of CAB+RPV LA, last visit or death, whichever occurs first, an on-treatment approach to analysis. Sensitivity analyses will use an intent to treat approach and virologic outcomes will be assessed regardless of regimen discontinuation.

We will perform additional sensitivity analysis limited to those who start CAB+RPV LA with resistance data available, to confirm no present or past evidence of viral resistance to, and no prior virological failure with agents of the NNRTI and INSTI class.

AIM 4. Monitor for resistance and next treatment response among individuals who switched off CAB+RPV LA regimen

Monitoring for resistance

Since this is a non-interventional study aiming to capture individual care in real world setting, the study will not mandate resistance testing following discontinuation of the regimen of interest. Health care providers following the local treatment guidelines decide

what laboratory and resistance tests are to be conducted. Data thus generated will be captured and analyzed by the study team.

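### Aim 3 reads failure at fixed time points with censoring at discontinuation, so failures that end treatment between windows are not counted; the models' follow-up limit and the viral-load fallback also need repair

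*Protocol*

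**What the plan says.** Section 8.6 (Aim 3) estimates the "proportion with virologic failure during the first six months and at six, twelve and twenty four months after the start of the treatment". Only the first of these is worded as a period. The others are read at a date, within 6 weeks either side. If no value is available, the plan uses "the first measurement during first six months, after 6, 12 or 24 months (and at most 6 weeks after the measurement".

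The primary approach is on-treatment: "Our primary analyses of virologic outcomes will censor follow-up at discontinuation of CAB+RPV LA, last visit or death, whichever occurs first". An intent-to-treat version is a sensitivity analysis.

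For the regression work, "Multivariable logistic regression models will investigate the factors associated with virologic failure at 6 months, 12 months and 24 months after CAB+RPV LA initiation". Two sentences restrict who enters: "Detailed analysis of additional risk factors will be limited to persons with 6, 12 or 24 months of follow-up", and, after the rule that "Multivariate analyses will be performed when > 30 persons on CAB+RPV LA have virologic failure", the statement that "analyses will be limited to persons with > 6-, 12- or 24-months follow-up".

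Section 8.3.2 defines confirmed virologic failure (CVF) in two ways: two consecutive viral loads (VL) of at least 200 copies/mL, or one such value with "regimen discontinuation within 4 months of VL" of it. Section 8.3.1 runs follow-up for data analyses from first injection to as long as 48 months after discontinuation.

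**The concern.** Objective 3 (Section 7) asks what proportion of people who initiate the regimen experience virologic failure. Failure is itself a reason to stop, and the second CVF limb contains stopping as part of its definition. An analysis that ends follow-up at stopping and then looks only around fixed dates can lose the events it is meant to count.

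If so, the 12- and 24-month results describe people still on treatment rather than those who started, and the distortion runs towards less failure. In the models, entry would depend on the outcome, so risk-factor estimates would come from a selected subset of failures. If the fallback adds no values, people without a VL in the window have no outcome at that date.

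**Working it through.** **1. Window coverage.** Six weeks is 42/30.44 = 1.38 months, and 2 x 6 = 12 weeks reproduces the stated window width. The windows are:
- 6 months: 4.6-7.4
- 12 months: 10.6-13.4
- 24 months: 22.6-25.4

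Adding the cumulative period (months 0-6) leaves 7.4-10.6 (3.24 months) and 13.4-22.6 (9.24 months) uncovered: 12.48 of 25.38 months, or 49%. A person who fails and stops inside either gap is censored before the next window opens and is a failure in no primary proportion.

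*Rough size (assumptions).* Let failures be spread evenly over the 25.38 months, let a share p of them stop between 0.5 and 4 months later (uniform), and ignore other stopping. The expected time in each gap at which a failure would also stop before the next window is:
- first gap: (3.24 - 0.5)^2 / (2 x 3.5) = 1.07 months
- second gap: (9.24 - 4) + 3.5/2 = 6.99 months

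(1.07 + 6.99)/25.38 = 0.32, so about 0.32 x p of failures appear in no primary proportion: 19% at p = 60%, 29% at p = 90%, none at p = 0.

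**2. The second CVF limb and the model restriction.** If the VL of at least 200 falls at month v, stopping is no later than v + 4. If follow-up means time on treatment, more than 24 months requires v > 24 - 4 = 20, and more than 12 months requires v > 12 - 4 = 8. Every second-limb failure before month 20 (or month 8) is then outside the 24-month (or 12-month) model. First-limb failures are excluded too when the person stops before the time point.

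**3. Share of failures kept (assumptions).** Take failure at 0.02 per year and other stopping at 0.10 per year, both exponential; a share p of failures stops 0.5-4 months later (uniform). None of these values is in the protocol.
- Failure by 24 months while on treatment: (0.02/0.12) x (1 - e^(-0.24)) = 3.56%.
- Kept if failure never leads to stopping: e^(-0.20) x (1 - e^(-0.04)) / 0.0356 = 0.0321/0.0356 = 90%.
- Kept if it always does: only failures shortly before month 24 survive. The mean delay is 2.25 months (0.1875 year), giving about 0.02 x 0.819 x 0.1875 x 0.963 / 0.0356 = 8%.
- In general: (1 - p) x 0.903 + p x 0.083.

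| Share of failures that stop (p) | 24-month failures with more than 24 months on treatment |
|---|---|
| 0% | 90% |
| 30% | 66% |
| 60% | 41% |
| 90% | 17% |
| 100% | 8% |

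*Effect on the more-than-30-failures rule, if counted in the restricted set.* With all failures kept, 31/0.0356 = about 870 starters are needed. At p = 60% it is 31/(0.0356 x 0.41) = about 2,100. The largest sample size in Table 4 is 1,000.

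**4. Fallback.** The window is [T - 6 weeks, T + 6 weeks]. Read as the first VL after T and no more than 6 weeks later, the fallback is (T, T + 6 weeks]. Every day of it is already in the window, so it adds 0 days at 6, 12 and 24 months. For the first six months, the fallback is again a value from those six months.

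**The case against.** **The follow-up limit does not govern the primary proportions.** This stands. Both restricting sentences concern risk-factor and multivariable analyses. A reader might infer that the primary proportions are computed only in people with more than 24 months on treatment; the text does not say so. The problem with the proportions comes from censoring combined with point-in-time windows.

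**Follow-up may not mean time on treatment.** Under Section 8.3.1, people who fail and stop would still meet the limit and stay in the models. This also stands as far as it goes, so it cannot be said flatly that such failures never qualify. But Section 8.6 explicitly ends follow-up at discontinuation for the primary virologic analyses, so the protocol supports two incompatible readings.

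**In the second limb the VL comes before the stop, and failure at 12 months could mean by 12 months.** Possible, but the plan separates failure during the first six months from failure at the later dates and sets a window around each date. The cumulative reading has to be supplied by the reader.

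**These failures are visible elsewhere.** Partly. Reasons for discontinuation, including virological failure, are tabulated, and early failure is cumulative. The intent-to-treat analysis keeps people who stopped. Read at a time point, however, it counts someone who failed at month 8 and re-suppressed on the next regimen as a success at month 24. None of these gives cumulative failure by 12 or 24 months.

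**The fallback wording is garbled.** True: its 6-week limit is tied to the measurement, not to the date. The finding of no added value depends on reading it as the target date. How many people lack a VL in the window cannot be derived, because VL frequency is not given and visits are tied to injections and scheduled forms.

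**Conclusion.** The point holds in this form. As written, the primary 12- and 24-month proportions miss failures that end in stopping between windows, and they understate failure whenever some who fail then stop. Under the on-treatment definition, the models also exclude failures that led to stopping before the time point, including all second-limb failures before month 8 or month 20. Under the Section 8.3.1 definition they would not, and the protocol does not settle which applies.

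The direction follows from the text; the size does not. It turns on the share of failures that stop: 24-month retention runs from about 90% to 8% across the possible range, with failure and other-stopping rates assumed. A reader might infer that the models lose most of their events. That is true only if more than about half of failures stop, which the protocol neither states nor excludes. The fallback is empty on its natural reading.

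**What to change.** - **Proportions:** report cumulative CVF by 6, 12 and 24 months from first injection among all per-label CAB+RPV LA starters. Count CVF on treatment, or leading to discontinuation, as an event. Treat stopping without failure and death as competing events (for example, Aalen-Johansen).
- **Models:** keep anyone with CVF before the time point as an event whatever the later follow-up, or model time to CVF.
- **Follow-up:** reconcile Sections 8.3.1 and 8.6 and state which definition the limit uses.
- **Time-point suppression:** keep these proportions as planned.
- **Fallback:** replace it with the VL nearest the target date in a window wider than 6 weeks either side (for example, 3 months either side), or delete it.

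The cost is wording in the protocol and any analysis plan; no new data are required. Reported failure may be higher, and the timing of fallback values will be less exact.

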6. RATIONALE AND BACKGROUND

6.1. Background

Cabotegravir (CAB), a human immunodeficiency virus type-1 (HIV-1) integrase strand transfer inhibitor (INSTI), in combination with Rilpivirine (RPV), an HIV-1 non-nucleoside reverse transcriptase inhibitor (NNRTI), is indicated as a complete regimen for the treatment of Human Immunodeficiency Virus type 1 (HIV-1) infection in adults who are virologically suppressed (HIV-1 RNA <50 copies/mL) on a stable antiretroviral (ART) regimen without present or past evidence of viral resistance to, and no prior virological failure with agents of the NNRTI and INSTI class. Prior to the initiation of CAB long acting (LA) injection, CAB tablets together with RPV tablets should be taken for approximately one month (at least 28 days) to assess tolerability to CAB and RPV.

Treatment with CAB+RPV LA should be prescribed by a physician experienced in the management of HIV infection. Each injection should be administered by a healthcare provider (HCP). Prior to starting the regimen, the HCP should carefully select individuals who agree to the required injection schedule and counsel individuals about the importance of adherence to scheduled dosing visits to help maintain virologic suppression and reduce the risk of viral rebound and potential development of resistance associated with missed doses. Following discontinuation of CAB+RPV LA injection, it is essential to adopt an alternative, fully suppressive ARV regimen per the summary of product characterization (SmPC).

The Marketing Authorization Holders (MAH) propose a five-year Drug Utilization Study (DUS) to be conducted in a real-world clinical setting. This prospective observational cohort study will aim to better understand the individual population receiving CAB and/or RPV LA containing regimens in routine clinical practice, usage patterns, adherence, post marketing clinical effectiveness of these regimens and monitor for resistance among virologic failures for whom data on resistance testing are available.

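### No planned virologic analysis keeps a failure on CAB+RPV LA followed by a switch as a non-success at 12 or 24 months: the primary analysis censors it and the intent-to-treat check reads viral load on the next regimen

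*Protocol*

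**What the plan says.** Protocol section 8.3.2 (Clinical effectiveness) sets three virologic measures:

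- "Proportion of individuals, virologically suppressed/undetectable (<50 copies/mL) at 6, 12 and 24 months following initiation of CAB+RPV LA regimen"
- "Proportion of individuals with VL <200 copies/mL at 6, 12 and 24 months following initiation of CAB+RPV LA regimen"
- "Proportion of individuals with confirmed virologic failure (CVF) during the first 6 months, and at 6, 12 and 24 months"

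CVF has two routes. The first is "Two consecutive HIV RNA VL levels ≥200 copies/mL or" the second, which is a single value at or above 200 copies/mL with the regimen stopped within 4 months.

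Section 8.6 (Aim 3) says how the time points are read: "a window of 12 weeks around the date in question will be used for virologic failure", that is, ±6 weeks, with a fallback to a later measurement if none falls inside.

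On discontinuation, section 8.6 has two rules. For the primary analysis: "Our primary analyses of virologic outcomes will censor follow-up at discontinuation of CAB+RPV LA, last visit or death, whichever occurs first". For the sensitivity analysis: "Sensitivity analyses will use an intent to treat approach and virologic outcomes will be assessed regardless of regimen discontinuation".

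Section 6.1 states what is expected after stopping: "Following discontinuation of CAB+RPV LA injection, it is essential to adopt an alternative, fully suppressive ARV regimen". Response to that next regimen has its own analysis under Aim 4.

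Nowhere does the protocol say that a CVF met on CAB+RPV LA persists to later time points. Nor does it say that a stop for failure counts as non-success at a later visit.

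**The concern.** The weak point of an on-treatment analysis is that people who fail tend to stop, and censoring at the stop removes them from later visits. A sensitivity analysis on discontinuation should show how much that matters.

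The check chosen here brings these people back, but with the viral load they have on other drugs. Because the protocol expects those who stop to move to a suppressive regimen, many may be suppressed by the next visit. Objective 3 asks what proportion of people who start CAB+RPV LA experience virologic failure. For failures after month 6, no stated virologic analysis gives that proportion at 12 or 24 months unless CVF is read cumulatively, and the text does not say that it is.

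**Working it through.** **Step 1. One person, outcome by outcome.** Take a person who meets CVF at month 8, stops at month 10 and has a viral load below 50 copies/mL on other drugs at month 12.

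| Measure | Primary (on-treatment) | Intent-to-treat |
|---|---|---|
| <50 and <200 at month 12 | censored, absent | suppressed |
| CVF at month 12, read in the ±6-week window | censored, absent | not a failure |
| CVF at month 12, read as failure by month 12 | failure | failure |

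Had the same person met CVF at month 4, CVF during the first 6 months would keep the failure in both analyses, because it covers an interval. The <50 and <200 measures at later visits would still score the person as suppressed under intent-to-treat.

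**Step 2. Which reading of CVF at 12 and 24 months?** Section 7 (objective 3), section 8.3.2 and section 8.6 each set the first-6-months measure apart from the measures at 6, 12 and 24 months. Section 8.6 attaches a ±6-week window to the latter. This favours the point-in-time reading but does not settle it.

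**Step 3. Static illustration.** The sample size and failure proportion come from Table 4 (N = 500, P = 0.05, so 25 failures). The exact Clopper-Pearson limits are 0.0326 to 0.0729, which reproduces the stated 0.033 to 0.073. The number *m* who have switched and re-suppressed before the visit is assumed.

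- Carried forward: 25/500 = 5.0%.
- Read at the visit, intent-to-treat: (25 − m)/500.
- Read at the visit, on-treatment: (25 − m)/(500 − m), if only those *m* have stopped.

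| m | Intent-to-treat at the visit (exact 95% CI) | On-treatment at the visit |
|---|---|---|
| 0 | 25/500 = 5.0% (3.3 to 7.3%) | 25/500 = 5.0% |
| 6 | 19/500 = 3.8% (2.3 to 5.9%) | 19/494 = 3.8% |
| 13 | 12/500 = 2.4% (1.3 to 4.2%) | 12/487 = 2.5% |
| 19 | 6/500 = 1.2% (0.4 to 2.6%) | 6/481 = 1.2% |
| 23 | 2/500 = 0.4% (0.05 to 1.4%) | 2/477 = 0.4% |

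The closeness of the last two columns follows from the simplification that everyone who stopped has re-suppressed. It is not evidence about the real data.

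**Step 4. Illustration with timing.** None of these inputs is in the protocol: CVF hazard λ = 0.01, 0.02 or 0.03 per year; other stops μ = 0.10 per year; stop 2 months after CVF; a share r = 0.80 to 0.95 of those who switch re-suppressed 3 months after the stop. Let s = λ + μ.

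- Cumulative CVF by 24 months: C = (λ/s)(1 − e^(−2s)).
- CVF in the last 5 months (2 + 3), so still viraemic: R = (λ/s)(e^(−19s/12) − e^(−2s)).
- Viraemic at 24 months on any regimen: V = R + (1 − r)(C − R).

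For λ = 0.01:

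- C = 0.0909 × (1 − 0.8025) = 1.80%.
- R = 0.0909 × (0.8402 − 0.8025) = 0.34%.
- V = 0.34 + 0.05 × 1.45 = 0.41% at r = 0.95, and 0.34 + 0.20 × 1.45 = 0.63% at r = 0.80.

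| λ per year | C | V | V/C |
|---|---|---|---|
| 0.01 | 1.8% | 0.4 to 0.6% | 23 to 35% |
| 0.02 | 3.6% | 0.8 to 1.2% | 23 to 35% |
| 0.03 | 5.3% | 1.2 to 1.8% | 23 to 35% |

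C and V are different quantities, one cumulative and one at a point in time, so some gap between them is built in. The table shows how far apart the two readings of CVF at 24 months could lie under these inputs.

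**The case against.** Five points can be made on the other side.

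1. *Assessing outcomes regardless of discontinuation is a recognised treatment-policy approach and suits an objective framed around people who initiate the regimen.* This stands. A reader might infer that the intent-to-treat analysis is an error, and the protocol does not support that. The gap lies in what is missing beside it.
2. *CVF during the first 6 months keeps early failures, and the second CVF route counts a raised viral load followed by a stop as failure.* This stands, and it limits the point to the <50 and <200 measures and to CVF at 12 and 24 months. The second route defines the event but does not say whether it persists to a later visit.
3. *CVF at 12 and 24 months may be meant cumulatively.* This is possible. One sentence in section 8.3.2 would then settle CVF in both analyses, though the <50 and <200 measures would be unchanged.
4. *Failure-related stops are reported elsewhere.* Section 8.3.2 has all discontinuations tabulated, reasons are coded in Table 3, durability is given at 6, 12 and 24 months, and Aim 4 covers resistance and next-regimen response. This stands. It is why one should not say that the analysis hides failures: a reader would see these stops next to the virologic figures, though not combined into one virologic outcome.
5. *The size is assumed throughout.* This stands too. It is tempting to add that the two analyses would agree and so make a low failure figure look robust. The documents do not show that. With the inputs of step 4, a windowed on-treatment figure is about λ × (2 months + 12 weeks) = λ × 0.397 years = 0.4, 0.8 and 1.2%. The intent-to-treat figure is level with it or higher, depending on r.

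**Conclusion.** The concern holds in a limited form. For the <50 and <200 copies/mL measures, the intent-to-treat analysis scores a person who failed, switched and re-suppressed as suppressed, and the primary analysis has already censored that person. For CVF at 12 and 24 months the same follows on the point-in-time reading, which the wording favours without settling it. CVF during the first 6 months is not affected.

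The treatment-policy analysis is sound for its own question. It does not test failure-related censoring, and no other stated virologic analysis counts failure followed by a switch as non-success at 12 or 24 months. The plan as written can therefore understate failure among initiators at those visits.

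The direction requires only that some people who fail re-suppress on another regimen before the visit. The size cannot be derived from the protocol, and the figures above are illustrative. This is an inexpensive improvement that should be made, not a fault that invalidates the plan.

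**What to change.** - In sections 8.3.2 and 8.6 (Aim 3), state that a CVF met on CAB+RPV LA counts as failure at that and every later time point, cumulative from the first injection.
- Add one supplementary analysis of the <50 and <200 copies/mL measures in which a stop for failure or resistance (Table 3 codes 1, 1.1, 1.2 and 1.5) counts as not suppressed at later visits. Code 1 also covers immunological and clinical failure, so show it as a separate line.
- Keep the existing intent-to-treat analysis and label it treatment-policy.

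The cost is a few sentences and one extra table. The dates, viral loads and stop reasons are already collected. The failure figure will be slightly less favourable.
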